The proposed PROCure Recovery patient-facing mobile app will leverage the power of two established evidence-based approaches (i.e., contingency management and self-monitoring) to incentivize recovery and increase adherence to buprenorphine, engagement in care plans, as well as participation in routine outcomes monitoring. The PROCure Recovery mobile app offers providers real-time, clinically meaningful patient-reported outcomes data in accordance with best practices (measurement-based care) and national standards. Patients can earn both non-monetary and monetary-rewards (via funds deposited to a smart debit card blocking cash withdrawals and purchases at certain vendors) for medication adherence, engagement in care, and completing outcomes monitoring surveys. Remote adherence tracking and electronic outcomes monitoring extends care management and coordination outside the treatment facility or provider's office and into the patient's home. Based on trends in patient-reported outcomes collected remotely, providers can modify the care plan accordingly in real-time.

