### **Study Aim**

Specific Aim: *Study preliminary effectiveness of PROCure Recovery on medication adherence, engagement in care, participation in remote patient monitoring, and clinical health outcomes.* A 4-week, randomized proof-of-concept pilot study will be conducted. Primary outcomes (and endpoints) include rates of: buprenorphine adherence (>90% daily doses; [14]), care plan adherence (>50% of weekly care plan activities; [53]), and participation in daily outcomes monitoring surveys (>90%; [44]) using a combination of patient/provider self-report and verification via app/dashboard, GPS location tracking data (to confirm attendance at outpatient appointments), and clinic urinalysis drug screen (UDS) results.

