Procedures: A 4-week, randomized proof-of-concept pilot study will assess the feasibility, acceptability, and effectiveness of the PROCare Recovery app. Participating providers will be trained on the PROCare app prior to enrolling patients. Eligible patients will complete an electronic informed consent form prior to enrollment in the trial. Participants will complete baseline measures of study outcomes. Patients will be oriented to the app at the outset of treatment during the induction phase and continued throughout the 4-week trial. Remote patient outcomes data will be collected during treatment and at the end of the study via the PROCare app, which will include the same measures completed at baseline. Following 4-week participation, patients will be contacted to provide qualitative/quantitative feedback on PROCare usability.

Primary outcomes (and established endpoints) include rates of: buprenorphine adherence ( $>90\%$  daily doses [14]), care plan adherence ( $>50\%$  of weekly care plan activities [54]), and participation in daily outcomes monitoring surveys ( $>90\%$  [45]) using a combination of patient/provider self-report and verification via app/dashboard, clinic UDS results, and GPS location tracking data (to confirm attendance at outpatient appointments). Pre/post change in the secondary outcomes will be assessed using validated measures: opioid/other substance use (days of use), craving (Opioid Craving Scale [63]), motivation (Readiness Ruler [64, 65]), self-efficacy (Brief Situational Confidence Questionnaire [70]), quality of life (WHO EUROHIS Quality of Life Scale [66]), DSM-5 OUD diagnostic criteria [71], depression (Patient Health Questionnaire-9 [PHQ-9])/anxiety (General Anxiety Disorder-7 [GAD-7]). The System Usability

Scale [72] will be used to objectively quantify the usability of the PROCare prototype using a naive sample (Aim 2 sample is distinct from Aim 1 sample). Participants assigned to the PROCare group will also be asked to complete ultra-brief daily check-in measures. Additional information collected from PROCare participants will include activity data within the app (e.g., clicks, timing). Pre/Post data will be entered into a web form on tablet, laptop, or mobile device, and immediately sent (and stored), item-by-item, to the cloud platform that is hosted in a HIPAA secure physical and software environment. The entered data is visible to the participant in the screen of the device at that time, but is not stored locally.

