
Participants in both conditions (PROCare and treatment as usual/control) will receive \$50 for their study participation. As stated in the consent form, participants will only receive the \$50 gift card after they complete the 4-week follow-up. In order to receive the \$50, the participant must complete both the baseline and follow-up measures. Patients allocated to the PROCare group will have the opportunity to earn an additional \$150 in monetary incentives over the course of the 4-week trial based on their level of participation in various activities using the app (competing brief daily check-in surveys, reading psychoeducational materials in the content library, answering questions about adherence to their buprenorphine medication, attending treatment appointments, etc.). Participants in the PROCare group will receive monetary incentives using a smart debit card (*True Link*), which has a feature that can block purchases from certain vendors (liquor stores, etc.) and also block cash withdrawals. True Link smart debit cards have been used to good effect in numerous addiction treatment settings and similar reward-based research studies, and represent the most feasible option relative to cash payments. Due to randomization, participants will have an equal chance of being allocated to the PROCare group and having the opportunity to earn additional incentives. The amount of additional incentives for completing various activities within the app (\$150) is consistent with other similar reward-based substance use disorder apps.

**Statistical Analysis Plan:** Consistent with best practice guidelines for pilot trial sample size calculations with a medium effect size [73, 74] the proposed pilot study will attempt to include a minimum of 15 participants per arm. Accounting for an expected 30% attrition rate, we will attempt to recruit 40 patients. Independent samples t-tests and Pearson's chi-squared tests will determine mean differences on continuous and dichotomous variables, respectively.

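### The primary endpoint of more than 90% of daily buprenorphine doses has no described source that counts doses independently of the patient, and the only described app dose measure exists in one arm

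*Combined protocol and SAP*

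**What the plan says.** The Study Aim section lists three primary outcomes. The first is "buprenorphine adherence (>90% daily doses; [14"]). The others are care plan adherence and participation in daily monitoring surveys. The follow-up is short: "A 4-week, randomized proof-of-concept pilot study will be conducted".

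One source list serves all three outcomes. The Procedures paragraph of Study Procedures & Statistical Analysis Plan says they are obtained "using a combination of patient/provider self-report and verification via app/dashboard, clinic UDS results, and GPS location tracking data (to confirm attendance at outpatient appointments"). Only GPS is given a purpose.

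On what the app records about dosing, the compensation paragraph of the same section gives one item among the rewarded activities: "answering questions about adherence to their buprenorphine medication". The Procedures paragraph adds that "Additional information collected from PROCare participants will include activity data within the app (e.g., clicks, timing"). Study Purpose also states that "Remote adherence tracking and electronic outcomes monitoring extends care management and coordination outside the treatment facility", but gives no mechanism for the tracking.

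The daily check-ins, and up to $150 of incentives for app activity, belong to the PROCare arm only. Both arms receive $50 for completing the baseline and 4-week measures.

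**The concern.** The endpoint needs doses taken, but the described sources may deliver only doses reported. Nothing says who counts doses, from what record, or what happens when two sources disagree. The cut-off leaves room for two missed doses in 28, so a few misreported days can move a patient across it.

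The comparison is more exposed than the rate. The app questions, the provider's view of the answers and the extra incentives exist only in the PROCare arm, and patients necessarily know whether they have the app. How doses are counted for controls is not described. Both the measuring instrument and the motive to give a favourable answer may therefore differ by arm. A difference in reporting would then look like an effect of the app on adherence, which is what the trial sets out to show.

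**Working it through.** The plan states no figure for reporting accuracy, so there is none to reproduce. The check has a textual part and an illustrative part.

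**1. What each listed source is described as doing for doses**

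| Source | Described role | Counts daily doses? |
|---|---|---|
| Patient self-report | Unspecified; in the app, answers to adherence questions | Only as the patient reports |
| App/dashboard | Those answers, check-ins, and click and timing logs; the dashboard shows providers patient-reported data | Not independently of the patient |
| Provider report | Named only | Not described |
| Clinic UDS | Named only; Background mentions drug-free screens; no buprenorphine assay, schedule or conversion rule | Not described |
| GPS | Appointment attendance | No |

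No pill count, dispensing record, observed or video dosing, or electronic cap is described.

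**2. Threshold.** Assume one dose a day for 28 days. Then 25/28 = 89.3% fails and 26/28 = 92.9% passes, so the endpoint is X ≥ 26.

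**3. Effect on the rate.** Let p be the true daily probability of taking the dose and f the share of missed doses reported as taken. The documents give neither. With independent days and identical patients, reported doses follow Binomial(28, q), where q = p + (1 − p)f. For example, p = 0.80 and f = 0.25 give q = 0.80 + 0.20 × 0.25 = 0.85. The share classed adherent, P(X ≥ 26), is:

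| p | f = 0 | f = 25% | f = 50% | f = 75% |
|---|---|---|---|---|
| 0.70 | 0.4% | 3.3% | 18.7% | 64.9% |
| 0.80 | 6.1% | 18.7% | 45.9% | 83.7% |
| 0.85 | 18.7% | 37.6% | 64.9% | 91.4% |
| 0.90 | 45.9% | 64.9% | 83.7% | 96.8% |

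**4. Effect on the arm difference.** Take no true difference, mean daily adherence of 80% in both arms, f = 50% in one arm and f = 25% in the other. To let adherence vary between patients, draw each patient's p from a Beta(a, b) distribution with a = 0.8(1/ρ − 1) and b = 0.2(1/ρ − 1), where ρ is the within-patient correlation (assumed). Reported doses are true doses plus Binomial(missed doses, f).

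| ρ | Truly ≥ 26 | f = 25% | f = 50% | False difference |
|---|---|---|---|---|
| 0 | 6.1% | 18.7% | 45.9% | 27.2 points |
| 0.1 | 25.7% | 35.9% | 53.0% | 17.1 points |
| 0.3 | 45.7% | 51.7% | 61.0% | 9.3 points |
| 0.5 | 58.2% | 61.7% | 67.1% | 5.4 points |

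The false difference shrinks because, when adherence clusters by patient, fewer patients lie just below the cut-off.

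**5. Effect on the test.** This uses exact enumeration of the planned Pearson chi-squared test with 15 per arm, at an assumed two-sided 5% level, with no true difference. If 50% are truly adherent and 30% of the non-adherent app patients alone are classed adherent, the app-arm rate is 0.50 + 0.50 × 0.30 = 65%, and the false-positive rate rises from 4.6% to 12.5%. If 31% are truly adherent, it rises from 5.4% to 20.3%. If both arms over-report equally (30%), it stays near 5% (5.2% and 4.6%): the rates are inflated but the test of no difference keeps its level.

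**The case against.** Several stronger readings are tempting, and the documents do not support them.

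- **No listed source could contradict a patient who reports 28 of 28 doses.** Provider report and clinic UDS are both listed. A source need not count doses to cast doubt on a perfect report, and whether the UDS detects buprenorphine is simply not stated. The supportable statement is that no source is described as counting doses independently of the patient.
- **The plan passes off app answers as verification of doses.** The sentence covers three outcomes at once. App verification suits survey participation well, and the plan openly names self-report as a source. The list of app activities is open-ended, and the remote adherence tracking is unspecified. The defect is that sources are not mapped to outcomes.
- **Patients are paid for saying that they took their dose.** The compensation paragraph pays for participation, including answering the questions, while Study Purpose describes rewards for adherence itself. Which applies is unclear.
- **The bias is 27 points.** That figure needs independent doses and identical patients, an assumed over-reporting gap between arms, and no correction from provider report or UDS. Modest between-patient variation reduces it sharply.

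It is also fair to say that self-report is a defensible choice in a 4-week proof-of-concept study, and that the 4-week measures may include a dose question for both arms. The documents do not say so.

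What stands is that the dose count rests on the patient's word as far as the plan describes it, and that the described app measure exists in one arm only.

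**Conclusion.** The point holds as a gap in measurement. Followed as written, the plan can measure this primary endpoint differently in the two arms, with no described same-source check. The direction is clear: over-reporting raises the adherence rate, and unequal over-reporting biases the comparison towards the arm that over-reports more. Equal over-reporting inflates the rates without raising the false-positive rate in the cases calculated.

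The size cannot be derived from the documents. The range of about 5 to 27 points rests on 28 daily doses, 80% mean adherence, 50% versus 25% over-reporting and a correlation between 0 and 0.5, all of them assumed. It shows that the effect could matter; it is not an estimate. The documents do not establish that over-reporting will occur or that it will differ by arm.

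**What to change.** In Study Aim and in Procedures:

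1. Label app dose answers as patient-reported, and state that they are not verification of doses.
2. Ask one dose-recall question with the same wording and at the same time in both arms, for example at the existing 4-week follow-up. Daily app answers can still be described within the PROCare arm.
3. For every randomised patient, extract buprenorphine prescribing or dispensing dates and days' supply from the site record. Report days covered out of 28 by arm, beside the planned UDS results, as a check on the self-reported rate.
4. State in advance that, if the self-reported and record-based results disagree, any conclusion is limited to self-reported adherence.

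Supply should remain a check and not become a rule for counting doses within the primary endpoint. No daily dose report is described for controls to set against it, and a patient with 28 days' supply would still pass on self-report alone.

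The cost is a wording change, one question at an existing contact and one record extraction for about 40 patients. Access to the site record is assumed. Supply shows that medication was available, not that it was taken, and four-week recall is coarser than daily reporting. With the expected 30% attrition, recall could be missing for about 12 of 40 patients (0.30 × 40), whereas the record could still cover them.

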Another well-studied and effective intervention is self-monitoring, which in and of itself has been found to reduce substance use and related problems [27, 28]. Self-monitoring (also known as ecological momentary assessment [EMA] when field assessments utilize various devices) has been used as both a means to study behavior as well as a standalone intervention [29, 30]. Contingency management and self-monitoring have been around for decades, but they remain underutilized in the current digital health era. Many elements of these approaches are rudimentary, outdated, and onerous (requirement for in-person appointments, use of a “fish bowl,” paper-and-pencil, separate single-function device or electronic diary), which warrants the need for development of technology-enabled solutions that can leverage the power of these evidence-based approaches in a way that is viewed by patients/providers as acceptable and feasible relative to traditional methods. With automation, prompts, and a meaningful user-friendly interface, PROCare seeks to address traditional barriers that have precluded uptake and widespread adoption of these two effective approaches to increase medication adherence [19]. Although treatment lasting of 12 months is essential for long-term OUD recovery [35], most patients do not engage in treatment for the needed duration [14]. This creates a strong case for technology-enabled solutions to enhance adherence/engagement in treatment.

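### Daily-survey participation is a primary outcome under the effectiveness aim, but only the PROCare arm is asked for daily check-ins, so the stated two-sample tests cannot say anything useful about it

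*Combined protocol and SAP*

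**What the plan says.** **Aim and outcome.** The Study Aim section sets out to "Study preliminary effectiveness of PROCure Recovery on medication adherence, engagement in care, participation in remote patient monitoring, and clinical health outcomes". Among the primary outcomes it lists "participation in daily outcomes monitoring surveys (>90%; [44" (the quotation stops at a reference number). The Procedures paragraph of Study Procedures & Statistical Analysis Plan repeats the outcome with the same 90% endpoint. The other two primary outcomes are buprenorphine adherence and care plan adherence. The documents call the app both PROCure and PROCare.

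**Who is surveyed daily.** Procedures states: "Participants assigned to the PROCare group will also be asked to complete ultra-brief daily check-in measures". The compensation text lists "competing brief daily check-in surveys" (so spelled) among the activities that earn the PROCare group up to an additional $150. The comparison arm is treatment as usual. The $50 paid in both arms depends only on completing the baseline and follow-up measures.

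**Analysis.** The Statistical Analysis Plan paragraph gives the tests in one sentence: "Independent samples t-tests and Pearson's chi-squared tests will determine mean differences on continuous and dichotomous variables, respectively". It names no outcome, gives no scoring rule for controls and describes no one-arm estimate.

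**The concern.** A between-arm test needs a value for this outcome in both arms. Controls are not asked for the surveys, so their participation is either undefined or zero by design. In neither case can a comparison show whether the app increases participation in monitoring, which is what the aim sets out to study.

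One of three primary results is at stake. A small p-value could be reported as preliminary evidence of effectiveness when it reflects only who was handed the survey. If the tests are not meant for this outcome, the plan does not say how a primary outcome is to be analysed. Either way, the quantity the trial can measure well, the completion rate in the PROCare arm, has no stated estimate or interval.

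**Working it through.** The plan gives no expected rate, alpha or power for this outcome, so there is no figure of its own to reproduce. The check is what the stated tests would do.

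**Inputs from the plan**
- Duration: 4 weeks, or 28 days.
- Endpoint: more than 90%.
- Minimum per arm: 15.
- Recruitment target: 40 with an equal chance of allocation, so 40/2 = 20 per arm.
- Test for dichotomous variables: Pearson chi-squared.

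**Assumptions not in the plan**
- One check-in per day.
- The 90% endpoint is applied to each participant.
- Two-sided alpha of 0.05.
- Pearson test without continuity correction.
- In case B, controls scored as not meeting the endpoint.

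**Step 1: the endpoint in days.** 0.9 × 28 = 25.2, so a participant passes with at least 26 of 28 check-ins (26/28 = 92.9%; 25/28 = 89.3%).

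**Step 2, case A: controls missing.** Let a and b be the PROCare participants who pass and fail, c and d the same for controls, and N the total. Then

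χ² = N(ad − bc)² / [(a+b)(c+d)(a+c)(b+d)].

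With no control values, c + d = 0. The denominator is zero and the statistic does not exist. A t-test fails too, because there is no control mean.

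**Step 3, case B: controls scored zero.** With 4 of 15 against 0 of 15:

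χ² = 30 × (4×15 − 11×0)² / (15 × 15 × 4 × 26) = 108,000 / 23,400 = 4.62, p = 0.032.

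Fisher exact, two-sided: 2 × C(15,4)/C(30,4) = 2 × 1,365/27,405 = 0.0996.

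| PROCare passing | Controls | Pearson p | Fisher p |
|---|---|---|---|
| 3/15 (20%) | 0/15 | 0.068 | 0.224 |
| 4/15 (27%) | 0/15 | 0.032 | 0.100 |
| 5/15 (33%) | 0/15 | 0.014 | 0.042 |
| 3/20 (15%) | 0/20 | 0.072 | 0.231 |
| 4/20 (20%) | 0/20 | 0.035 | 0.106 |
| 5/20 (25%) | 0/20 | 0.017 | 0.047 |

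The smallest expected count with four passes is 2.0, so the Pearson approximation is poor here. Under Fisher, five passes are needed instead of four. The choice of test moves the threshold by one participant and does not change what is being compared.

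**Step 4: meaning.** At 4/15, 11 of 15 PROCare participants (73%) miss the plan's own endpoint, yet the stated test gives p<0.05. The zero in the control arm is fixed by the design and carries no information about behaviour.

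**Step 5: what a one-arm estimate gives.** Exact (Clopper-Pearson) 95% intervals: 10/20 = 50% (27% to 73%); 18/20 = 90% (68% to 99%).

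**The case against.** The best reply is that the analysis sentence is general. It pairs tests with types of variable and does not list outcomes. Procedures also collects in-app activity data and usability feedback, which can have no control value, and these are not exempted either. Silence therefore does not prove that a between-arm test of daily-survey participation is intended. Procedures names feasibility as an objective, so a one-arm 90% benchmark is a natural reading. This stands as far as it goes: application of the two-sample tests is an inference, and scoring controls zero is an illustration that no section proposes. It does not close the gap, because no one-arm analysis is written and the aim places participation in monitoring under effectiveness.

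A second reply is that the daily surveys may not be the check-ins, or that controls use the app too, since "Remote patient outcomes data will be collected during treatment and at the end of the study via the PROCare app" names no arm. That sentence sets no daily frequency, and the text goes on to say that these are the baseline measures. No other daily instrument is described. If controls were meant to use the app, that would need reconciling with a treatment-as-usual arm.

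A reader might also infer that asking and paying only one arm is a flaw. It is not: the prompts and rewards are the intervention.

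**Conclusion.** The point holds and should be fixed. As written, the only stated tests, applied to this primary outcome, either cannot be computed or merely show which arm was given the survey. In the zero-scored case, 4 of 15 or 4 of 20 participants passing (20% to 27%) is enough for Pearson p<0.05. Those figures depend on the assumptions listed with the calculation and describe a scenario, not a stated intention.

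Confidence is medium, because the two inferences (daily surveys are the check-ins; the general tests apply to them) are reasonable but not confirmed in the text available.

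Two stronger conclusions might be drawn. One is that the sponsor plans to claim effectiveness from a forced zero; no section says so. The other is that the outcome must lose its primary status; that is not needed. Increasing participation in monitoring is a stated purpose of the app, and a one-arm rate is a legitimate primary result for a proof-of-concept pilot if it is labelled as such.

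**What to change.** **Statistical Analysis Plan paragraph.** Add, for example: *Participation in daily check-ins will be estimated in the PROCare arm only, among all participants allocated to PROCare, as the proportion completing more than 90% of check-ins, with an exact 95% confidence interval. It will not be tested against control or interpreted as evidence of between-arm effectiveness.* If the 90% figure is meant as a group benchmark, replace the proportion with the mean percentage of check-ins completed per participant and its 95% confidence interval. The sponsor should choose one.

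**Study Aim and Procedures.** Describe the outcome as a PROCare-arm feasibility or engagement outcome. It may remain on the primary list if marked as one-arm.

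Giving controls a daily survey is not the suggested remedy. The Background section describes self-monitoring as active in its own right ("Another well-studied and effective intervention is self-monitoring, which in and of itself has been found to reduce substance use and related problems"), so it would alter the comparison arm.

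**Cost.** No new data or participants. One nominal between-arm primary comparison is lost, and the aim can no longer offer effectiveness evidence on participation in monitoring. The edits are short, but they touch a primary outcome and the aim, so they should be made as an amendment.

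### Recruiting 40 patients at the stated 30% attrition leaves an expected 28 (14 per arm), short of the plan's own minimum of 15 per arm

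*Combined protocol and SAP*

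**What the plan says.** All the inputs stand in the section Study Procedures & Statistical Analysis Plan, in the Statistical Analysis Plan paragraph and the paragraph on compensation just before it.

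- **Required number.** Citing pilot-trial guidance and a medium effect size, the plan says "the proposed pilot study will attempt to include a minimum of 15 participants per arm".
- **Attrition and target.** The next sentence reads "Accounting for an expected 30% attrition rate, we will attempt to recruit 40 patients".
- **Arms.** There are two: "Participants in both conditions (PROCare and treatment as usual/control) will receive" the same participation payment.
- **Allocation.** Patients are randomised so that "participants will have an equal chance of being allocated to the PROCare group", which gives about 20 per arm from 40.

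No other section gives a different target, attrition rate or number per arm. The plan states no significance level, power, standard deviation or assumed response rates.

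**The concern.** The recruitment target is presented as the required number after an allowance for attrition. A reader will take it that 40 recruits, less 30%, leave at least 15 per arm. They do not.

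The error is small, but the plan has nothing else to fall back on. With no power calculation or precision target, the minimum count per arm is the whole numerical basis for the recruitment figure. If the target does not meet that count under the plan's own attrition assumption, 40 has no support as written. The study could also recruit all 40 patients, see exactly the attrition it expected, and still finish below its stated minimum. The protocol's Background/Significance text describes early dropout as widespread in these treatment settings, so the attrition allowance deserves to be right.

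**Working it through.** **Inputs (all from the plan):** minimum 15 per arm; 2 arms with equal chance of allocation, so 30 in total; attrition 30%, so the proportion retained is 0.70; recruitment target 40.

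**1. Reproducing the stated 40.** The standard inflation is n/(1 − attrition).

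- In total: 30/0.70 = 42.9, rounded up to 43.
- By arm: 15/0.70 = 21.4, rounded up to 22, so 44 in total.

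Neither gives 40. Multiplying by 1 + attrition comes closer: 30 × 1.3 = 39 in total, or 15 × 1.3 = 19.5, rounded up to 20 per arm, so 40. That may be where the figure came from, but the plan does not show its calculation and nothing below depends on this.

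**2. Forward check.**

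| Recruited | Expected completers at 30% attrition | Per arm |
|---|---|---|
| 40 | 40 × 0.70 = 28.0 | 14.0 |
| 43 | 43 × 0.70 = 30.1 | 15.05 |
| 44 | 44 × 0.70 = 30.8 | 15.4 |

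**3. Attrition that 40 can absorb.** 1 − 30/40 = 25%.

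**4. Chance of reaching the minimum.** This step needs assumptions that the plan does not state: exactly equal arms, the same 30% attrition in both, and patients dropping out independently. The number retained in an arm of size m is then Binomial(m, 0.70), and the chance for both arms is the square of the chance for one.

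| Per arm recruited | P(one arm keeps ≥ 15) | P(both arms keep ≥ 15) |
|---|---|---|
| 20 | 0.416 | 0.416² = 0.173 |
| 22 | 0.671 | 0.671² = 0.451 |

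**5. Effect on sensitivity.** The plan states no significance level or power, so take a two-sided 5% t-test with 80% power for illustration. The detectable standardised difference is 1.06 with 15 per arm and 1.10 with 14 per arm, a change of 0.04. This describes continuous outcomes only. The primary outcomes are framed as rates against thresholds, and a standardised mean difference does not describe those.

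**The case against.** The strongest reply is that this hardly matters. The study is a 4-week proof-of-concept pilot, both numbers are worded as attempts, and the gap is one patient per arm. The detectable difference barely moves, and no inference turns on 14 against 15. The title of one of the two cited sample-size references names 12 per group as its rule of thumb, which 14 exceeds. The recruitment paragraph also provides for weekly review of recruitment and retention, with broader recruitment if shortfalls appear. All of this stands, and it limits the consequence. None of it makes 40 the right figure for 15 per arm at 30% attrition. A weekly check against a target that is itself too low need not flag a problem.

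One could read 15 per arm as patients randomised rather than patients completing. Then 30 recruits would suffice and the attrition allowance would serve no purpose, so that reading does not rescue the sentence.

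A fair point concerns the probabilities. They rest on the assumptions stated with them, and by the same measure 44 recruits reach 15 in both arms only 45% of the time. Inflating by 1/(1 − attrition) meets the minimum on average and does not guarantee it. The 17% therefore shows how far 40 is from securing a minimum, and 44 should not be presented as securing it either.

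**Conclusion.** The concern holds. At the plan's own 30% attrition, 40 recruits give an expected 28 completers (14 per arm) against a stated minimum of 30 (15 per arm). The target is 3 patients too low on the total calculation (43) and 4 too low for equal arms (44). This part uses only the plan's figures and the natural reading that 15 per arm is the number left after attrition.

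The 17% chance of keeping 15 in both arms is illustrative and depends on equal arms and independent, equal attrition. The practical effect on precision is slight. This is a plain arithmetic inconsistency that should be corrected; it does not threaten the trial.

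**What to change.** Change the sentence in the Statistical Analysis Plan paragraph in one of these ways:

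1. **Keep 40 and restate what it delivers.** For example: 40 patients will be recruited; with 30% attrition about 28 (14 per arm) are expected to complete. Replace the minimum of 15 with this figure, worded as an expected number and not as a new minimum, and check that the cited pilot guidance still supports it.
2. **Keep 40 and 15 per arm, and state the condition.** Say that 40 supports 15 per arm only if attrition is at most 25%. The 30% expectation in the same sentence must then be revised with a reason, or the shortfall at 30% acknowledged.
3. **Keep 15 per arm and 30%.** Raise the target to 44 (22 per arm), and say that this meets 15 per arm on expectation.

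The first two cost one sentence, no extra patients and a slightly less favourable stated figure. The third costs four more recruits.
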